10.4 Stopping Rules

There are no interim analyses planned that would allow for a determination of futility or overwhelming benefit. Study enrollment will be suspended under the following circumstances:

1. Serious Adverse Events. Study enrollment will be suspended in the event of a single serious adverse event that is determined to be unexpected and at least possibly related. If suspended, study recruitment will not continue until a determination has been made about whether the known risks of participation have changed and the BU Medical Campus/Boston Medical

Center IRB has made a finding that the risk/benefit ratio remains favorable given the possible newly identified risk.

2. Risk of intoxication. Subject recruitment will also be suspended if more than one subject of the first ten subjects enrolled is discontinued by the investigator due to intoxication during the alcohol self administration trial. Due to differences in alcohol tolerance, BAL is not a reliable measure of subjects potentially posing a safety risk. Medical staff will make a subjective determination of risk based on the subject's behavior. After 10 subjects have been enrolled, the trial will be suspended if there are more than 10% of subjects whose participation has been halted by the study team due to concerns about physical safety because of intoxication during the alcohol self-administration trial. If suspended for this reason, the study team will consider design changes to reduce the likelihood of this as a potential risk to study subjects. Recruitment would

resume when the BU Medical Campus/Boston Medical Center IRB has made a determination that proposed changes to the study design have an acceptable risk/benefit ratio.

11 Data Handling and Record Keeping

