Randomized subjects will receive 8 days of study medication at the time of randomization. A riboflavin tracer (50mg) will be added to each capsule to serve as an objective measure of medication adherence on the day of the alcohol challenge⁵⁶. Two bottles will be dispensed to each subject: 1) 11 pills of Lacosamide or placebo over-encapsulated with 50mg of riboflavin and 2) 3 Pills of lacosamide or placebo over-encapsulated with 50mg of riboflavin. Subjects will take 100 mg of lacosamide (or placebo) twice per day until day 7. On day 7 subjects will increase to 150mg twice daily. Based on the metabolism of this drug, we expect to be within range of 90% of steady state for a 300 mg daily lacosamide dose by day 8 when the alcohol challenge trial will occur which is consistent with the clinical dose range (300-400mg daily as monotherapy) of this drug when it is used for seizure disorders⁵⁷. Subjects who are not able to achieve the target dose due to adverse effects will be discontinued from the study.

								Self-
Dose	Day 1	Day 2	Day 3	Day 4	Day 5	Day 6	Day 7	Admin
AM		100mg	100mg	100mg	100mg	100mg	150mg	150mg
PM	100mg	100mg	100mg	100mg	100mg	100mg	150mg	

The seven-day period of medication titration will begin within a window of 6 days depending upon scheduling the alcohol challenge. Subjects may be randomized and instructed to start the medication up to 6 days later so that day 8 will conicide with the alcohol challenge appointment. Subjects will be given a brief phone reminder to start medication on Day 1. During the sevenday period of medication titration, subjects will be asked to answer a medication compliance question each day by smartphone using the REDCap data capture through a web-based portal⁵⁸. In addition to assessing medication compliance, subjects will also be asked to rate their craving for alcohol each day using the alcohol VAS. Subjects will receive a \$5 reimbursement on each day they complete the VAS and answer the medication compliance question using the REDcap web-based portal. Subjects will be contacted by telephone on day 3 of the medication titration period for an adverse event assessment.

Medication Visit #2

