After the 7-10 day washout period subjects will return to the lab to receive study medication prior to the alcohol challenge #2. Subjects will complete the same tests and interviews completed during the randomization visit (See appendix A for schedule of events). Based on the assessments at medication visit #2, subjects be discontinued for the following reasons: pregnancy, recreational drug use, evidence of non-compliance with study medication, suicidal thoughts or behavior, and use of a new medication that would make participation unsafe. Subjects will receive an 8-day supply of study medication and will be scheduled for the alcohol challenge #2.

Alcohol Challenge Trials 1 & 2: Subjects will return to the laboratory on day 8 of titration for each medication trial to complete the alcohol challenge. For safety reasons, subjects will be asked to arrange transportation plans (no driving) prior each of the alcohol challenge trials.

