There will be a 7-10 day washout period between alcohol challenge Trial 1 and medication visit 2. Based on the known half-life of lacosamide, all of the medication will be cleared within 7 days. The washout may extend to 10 days to accommodate the scheduling of Trial 2. Concomitant medications, urine drug screening, urine pregnancy testing, blood alcohol level will be assessed to determine eligibility to proceed with the challenge. Blood alcohol level must be 0.000 to continue with the study procedures. Urine collected for drug screening will be exposed to ultraviolet light as an objective test of medication compliance. If no fluorescence is observed in the urine sample the subject will be excluded from continuing with the challenge. Measures of drinking (TLFB), cravings, (OCDS and AUQ), and neurocognitive function (COWAT, WMSIII Spatial Span and Digit Span tests) will be collected to inform secondary outcomes. Subjects will be observed taking the morning dose of lacosamide (or placebo) on the day of the challenge (after compliance is confirmed via a urine screening). The peak plasma concentration of lacosamide should be reached approximately 60 minutes after administration. The alcohol self-administration session will begin no sooner than one hour after the administration of the observed 150mg morning dose. The alcohol self-administration will be conducted in the GCRU. The room will be a carpeted and furnished with a lounge chair, side table and television which allows access to popular streaming entertainment (e.g., Netflix, YouTube). A small unobtrusive camera is mounted in one corner to allow for monitoring without study staff being present in the room. The room has ready access to a bathroom. The alcohol self-administration is divided into four segments: 1) a 5-minute segment for the priming dose, 2) a 40-minute segment for observing alcohol's effects, 3) a 60-minute segment of alcohol self-administration (Block1) and, 4) a second 60-minute segment of alcohol self-administration (Block2) [see figure 2 for the alcohol self-administration Procedure].

Priming dose. Subjects will be given a priming drink designed to increase the subject's blood alcohol level (BAL) to 0.03g/dl, using the alcohol of their choice that is 24% Alcohol By Volume (ABV) or greater. The volume of alcohol will be calculated using an online

Figure 2: Alcohol Self-Administration Procedure								

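### After an unexpected, possibly related SAE, rule 1 in section 10.4 pauses only intake; it should also hold dispensing, dosing and alcohol challenges for randomised subjects until the IRB finding

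*Combined protocol and SAP*

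**What the plan says.** Section 10.4 opens by naming enrolment as the thing that stops. Rule 1 repeats this: "Study enrollment will be suspended in the event of a single serious adverse event", where the event is unexpected and at least possibly related. It continues: "If suspended, study recruitment will not continue until a determination has been made about whether the known risks of participation have changed", and the IRB has found the balance of risk and benefit still favourable. Subjects already in the study are not mentioned.

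Wider wording appears once, in the second tier of the intoxication rule: "After 10 subjects have been enrolled, the trial will be suspended if there are more than 10% of subjects" halted for intoxication. The term is not defined, and the sentence on resuming again speaks only of recruitment.

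Section 9 (Study Procedures) shows what lies ahead for a randomised subject:

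- Titration period: "Randomized subjects will receive 8 days of study medication at the time of randomization". Some hold the bottles before the first dose: "Subjects may be randomized and instructed to start the medication up to 6 days later".
- Medication Visit #2: "Subjects will receive an 8-day supply of study medication and will be scheduled for the alcohol challenge #2". The grounds for stopping at that visit are personal to the subject: "subjects be discontinued for the following reasons: pregnancy, recreational drug use, evidence of non-compliance with study medication", suicidality, or an unsafe new medication.
- Before each challenge: "Concomitant medications, urine drug screening, urine pregnancy testing, blood alcohol level will be assessed to determine eligibility to proceed with the challenge". These checks too concern the individual.

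**The concern.** Rule 1 accepts that one such SAE puts the balance of risk and benefit in doubt until the IRB has ruled. That doubt applies at least as strongly to someone taking lacosamide, or about to start it and then drink in the laboratory, as to someone not yet enrolled. The stated action protects the second group and leaves out the first.

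Section 6.2 says participation brings no direct benefit, so a pause withholds no treatment the subject needs. The stake is exposure of a few people to a possible new risk during a period when the plan itself regards the risk as unresolved.

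**Working it through.** **1. Does any other section require a hold?**

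| Place | What it provides | Required hold for other randomised subjects? |
|---|---|---|
| 6.1, risks of study medication | Staff may stop the dose of a subject who reports adverse effects | No: individual, by judgement |
| 6.1, overconsumption | Staff may halt a subject for impairment or a safety issue arising in a session | No: discretionary |
| 9, Medication Visit #2 and challenge checks | Subject-level eligibility | No |
| 10.2 | Mid-week call and challenge-day adverse event checks | No: detection only |
| 10.3 | Unanticipated Problems to the IRB in 2 days (fatal or life-threatening) or 7 days (others); safety monitors' recommended changes in 7 days | No: reporting only |

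Section 10.2 also uses enrolment for the start of participation, as distinct from its end, so the word does not naturally cover subjects already under way.

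**2. Timing.** For a non-life-threatening Unanticipated Problem the reporting limit is 7 days, and titration lasts 7 days. At the outer limit, a full course can pass before the IRB is told.

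**3. How many subjects?**

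Inputs: N = 28 (12.2) to 112 (section 2); 24 months for the whole study (section 2), taken as 730 days of even accrual; 7-day titrations and a 7 to 10 day washout; start delayed by up to 6 days (section 9). Assumed: all N randomised, half to each sequence.

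- Shortest stay after randomisation: 7 + 7 + 7 = 21 days.
- Longest: 6 + 7 + 10 + 7 = 30 days. Adding 14 days from baseline gives 44, the plan's own limit.

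Average number in a state = N × days in that state / 730.

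- Challenge still ahead: 28 × 21/730 = 0.81, to 112 × 30/730 = 4.60.
- Taking lacosamide (7 days): 28 × 7/730 = 0.27, to 112 × 7/730 = 1.07.
- On lacosamide or yet to start it: 7 to 13 days if lacosamide comes first, 21 to 30 if placebo comes first, so a mean of 14 to 21.5 days. This gives 28 × 14/730 = 0.54, to 112 × 21.5/730 = 3.30.
- Share of randomised subjects held: 21/730 = 2.9%, to 30/730 = 4.1%.

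The documents state no accrual period. If accrual took 12 months, every figure would double (1.6 to 9.2 with a challenge ahead; 5.8% to 8.2% held).

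**4. Power if held subjects do not complete.**

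Section 12.2 uses f = 0.25, correlation 0.6, two time points, alpha 0.05. Two-level within-subject F test: noncentrality = n × 2 × 0.25² / (1 − 0.6), with 1 and n − 1 degrees of freedom.

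| n | Noncentrality | Power |
|---|---|---|
| 28 | 8.75 | 0.814 |
| 27 | 8.44 | 0.798 |
| 26 | 8.13 | 0.782 |
| 25 | 7.81 | 0.765 |

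The plan's 28 is reproduced as the smallest n that reaches 0.8. At n = 112 the noncentrality is 35.0 and power exceeds 0.999. After losing nine (n = 103; 9.2 is the largest average above) it is still about 0.9999.

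**5. What a held subject forgoes (section 9, Subject compensation).** A subject held in the washout misses $20 (visit) + $80 (challenge) + $40 (both-challenge bonus) + 7 × $5 (daily surveys) + $10 (survey bonus) = $185, plus up to $24 for drinks left (half of $48). The $10 bonus is counted per period because the $418 total then adds up: 40 + 20 + 20 + 160 + 40 + 70 + 20 + 48.

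**The case against.** The case against is mainly about proportion.

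- **Protective action need not wait.** The 2- and 7-day limits are outer limits for telling the IRB. Staff can stop a dose, end a session or unblind at once. Sections 3.1 and 13 also bind the study to institutional policy, federal regulations and GCP guidance, which might require more. This stands: a reader might infer that randomised subjects are unprotected or that dosing must go on, and the documents do not say so. But none of the visible measures is a required hold tied to the SAE trigger, and the content of the outside policies cannot be seen.
- **The hold is blunt.** An SAE on placebo, or one arising from an alcohol session, would stop everyone's capsules. True, but the same event already stops enrolment, and the IRB finding can lift the hold. A prompt, documented decision by the investigator or safety monitor would be gentler, but it would leave to judgement for exposed subjects what rule 1 makes automatic for new ones.
- **A pause has a price for subjects.** One might read the absence of direct benefit as meaning that nothing is lost. The compensation section contradicts this. A subject stopped in mid-titration would also miss the near-steady-state target for day 8, and one on the longest schedule has no slack within 44 days. For them a hold will often mean withdrawal.
- **Power.** It is tempting to say that any lost completer takes the study below 0.8. That holds only at N = 28 with two time points. Section 12.2 expects power above 0.8 with four time points, and at 112 the loss is negligible.

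**Conclusion.** The point holds as a gap in the scope of rule 1 and is worth amending. The text pauses intake only, and nothing else in the document obliges the study to hold dispensing, dosing or challenges for randomised subjects before the IRB finding. That conclusion rests on the wording and not on the arithmetic.

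The numbers only give scale, conditional on a trigger. With a 24-month accrual period, on average 0.8 to 4.6 subjects have a challenge ahead, of whom 0.5 to 3.3 are on lacosamide or yet to start it. These figures depend on even accrual, equal sequences and all N being randomised. The gap does not make the trial's results invalid, and the documents do not show that staff would in fact continue dosing.

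**What to change.** Amend 10.4 to define suspension once. From the day an SAE is judged unexpected and at least possibly related until the IRB finding:

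1. no enrolment or randomisation;
2. no dispensing, including at Medication Visit #2;
3. no alcohol challenge;
4. subjects holding capsules are contacted promptly, told to stop and given an adverse event check.

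Use the same term in both tiers of the intoxication rule. State that held subjects are withdrawn, or resume only as the IRB finding permits, and that data from a completed period stay in the mixed model planned in 12.1. State also whether challenge and completion payments are honoured for subjects stopped by the hold; they should be.

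Stopping early adds no new withdrawal step, because the dosing schedule in section 8 already ends after the day 8 morning dose with no taper.

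The cost is a short amendment, a contact script, any protected payments, and possibly the second period of the 2.9% to 4.1% of randomised subjects held on average at a trigger (24-month accrual). If the target really is 28 completers, allowing replacement of held subjects would protect the planned power.

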11.1 Confidentiality

All staff will be fully trained in the procedures for protection confidential health information. To maintain subject confidentiality, study data will be coded on CRFs that are identified by a subject number only. Source records with identifying information and CRFs will be stored in double-locked space with access only by authorized staff. Data stored in the REDcap system have strong protections including file encryption and password access. Subject information will not be released without written permission. Upon approval of the study by an IRB, an application will be filed with NIAAA for a Certificate of Confidentiality.

11.2 Source Documents

Source documents in this study include:
Laboratory test results
Photocopies of the urine drug screening test result
ECG tracings
Subject locator form
Subject contact form

Data generated by the methods described in the protocol will be recorded in the subjects' source binder. Data may be transcribed legibly on CRFs for each subject or directly inputted into an electronic system or any combination thereof.

11.3 Case Report Forms

The study case report form (CRF) will be the primary data collection instrument for the study. All data requested on the CRF will be recorded. All missing data will be explained. If a space on the CRF is left blank because the procedure was not done or the question was not asked, a written explanation will be included to detail why the data was not recorded. If the item is not applicable to the individual case, a notation will be made. All entries on will be printed legibly in black ink. If any entry error has been made, to correct such an error, a single straight line will be drawn through the incorrect entry and the correct data will be entered closely to the original data. All such changes will be initialed and dated. There will be no erasures or white-out on CRFs. For clarification of illegible or uncertain entries, the clarification will be printed near the item, then initialed and dated. Electronic CRFs in the REDcap system will include an audit trail.

The CRFs that will be used in this study are: Demographics Concomitant Medications Lacosamide effects on alcohol self administration and craving in heavy drinkers

Version 3.12 3.11.19

Adverse Events

Birth Control Assessment

Urine Drug Screening

Vital Signs

Blood Alcohol Level

Time-line Follow-back

Pregnancy test

Birth control assessment

Medical History

Physical Examination

MINI diagnoses summary

Medication Compliance log

Eligibility

ECG

C-SSRS

CIWA-AR

OCDS

AUQ

VAS

COWAT

Digit Span

11.4 Study Records Retention

Study records will be retained for at least seven years after completion of the study.

12 Statistical Plan

12.1 Study Hypotheses and Planned Analyses

For our primary outcomes, separate analyses will be conducted on data collected during the Priming and Self-Administration periods of the test session.

Hypothesis	Planned Analyses
1. Subjects will consume	The volume of alcohol consumed during alcohol challenge trials 1 and
less alcohol during an	2 will be used to test the effect of lacosamide on alcohol consumption.
alcohol self-administration	We will use a mixed models repeated measures approach to test for
trial when receiving	differences between alcohol consumed between the lacosamide and
lacosamide compared to	placebo self-administration trials ⁶¹⁻⁶² . This data will be divided into
when they are receiving	first and second-hour blocks of self-administration. Within-subject
placebo.	factors for this analysis will include treatment and Time Block. Trial
	order will be used as covariate in these analyses to allow evaluation as
	to whether the order of treatments had a significant effect on the
	outcome. Appropriate covariance structures will be determined using
	Akaike's information criteria to evaluate the best model fit. Results
	analysis will be examined for both treatment effects and the Treatment
	x Time Block interaction results.
2. Subjects will report lower	Craving measures (AUQ and VAS) collected at 30-minute intervals
levels of craving as	during the self-administration trials will be used to test the effect of
measured by the Visual	lacosamide on alcohol craving. A mixed models approach will be used
Analog Scale (VAS) and the	to test for differences in craving between the lacosamide and placebo
Alcohol Urge questionnaire	self-administration trials. Within-subject factors for this analysis will
(AUQ) during the	include Treatment and Time Block. Trial order will be used as
lacosamide self-	covariate in these analyses to allow evaluation as to whether the order
administration trial	of treatments has a significant effect on the outcome.
compared to the placebo	
self-administration trial.	
3. There will be no	COWAT and Digit Span scores collected on the day of each self-
significant difference in	administration trial (prior to consumption) will be used to determine the
verbal fluency or working	effect of lacosamide on verbal fluency and working memory. A mixed
memory between trials of	model repeated measures approach will be used to test for differences
lacosamide and placebo.	in COWAT and digit span scores between the lacosamide trial and the
	placebo trial. Day and Treatment will be treated as within-subject
	factors.
4. Subjects will report lower	The alcohol VAS and the TLFB measurements during the seven-day
levels of craving and	period of medication titration will be used to determine the effect of
consumption during	lacosamide on craving and consumption. Mixed Models repeated
lacosamide administration as	measures approach will be used to test for differences in craving and
compared to placebo	consumption between the lacosamide and placebo trials. Treatment
administration.	will be used as within-subject factor. VAS measures taken on each of
	the seven days of medication titration, repeated measures mixed models
	analysis will be conducted with Day and Treatment as within-subject
	factors.

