4.2.2 Secondary Outcome Measures

Secondary outcome measures for this study include the effect of lacosamide on 1) cognitive

function, and 2) alcohol use and craving during the titration period. The Controlled Word Association (COWAT)⁴⁰ and the Wechsler Adult Intelligence Scale (WAIS-5)⁴¹ Spatial and Digit Span tests will be used to assess the effects of lacosamide administration on cognitive function. The Obsessive-Compulsive Drinking Scale (OCDS)⁴², and the alcohol VAS will be used to assess the effects of lacosamide on craving during the medication titration period.

5 Study Design

This is a double-blind, randomized, placebo-controlled, crossover design trial that will test the effect of lacosamide on alcohol self-administration and craving following a priming dose of alcohol. An established human laboratory self-administration procedure will be followed³⁸. The O'Malley self-administration procedure entails the administration of a priming drink followed by the presentation of four drinks on a tray which subjects may drink, or receive compensation for the drinks not consumed. After one hour the first tray of drinks is removed and subjects are then given the opportunity to consume a second tray of drinks. Confirmation of the validity of this approach as a method for screening for medications to treat AUD include the finding that pretreatment with naltrexone, which is an approved medication for treating AUD, significantly reduced alcohol consumption when the O'Malley self-administration procedure was used⁴⁵. Using this procedure, our group has found that the anticonvulsant zonisamide reduces alcohol consumption in non-treatment seeking social drinkers⁴³. We later confirmed that the administration of zonisamide decreases alcohol consumption in subjects with AUD in a doubleblind randomized clinical trial²⁵ as have other investigators⁴³. Testing lacosamide using O'Malley's self-administration procedure is the next logical step in drug development following positive findings that lacosamide reduces drinking in animal models. The human laboratorybased alcohol self-administration procedure is a cost effective and time-efficient method for testing novel drug candidates for AUD treatment⁶.

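### Hypothesis 3 on cognition predicts non-significance, so a failure to reject would count as support although it is not evidence of no impairment

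*Combined protocol and SAP*

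**What the plan says.** Hypothesis 3 in the Section 12.1 table begins "3. There will be no" and continues "significant difference in", followed by verbal fluency or working memory, comparing the lacosamide and placebo trials.

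The planned-analysis cell beside it is worded neutrally. COWAT and Digit Span scores from the day of each "administration trial (prior to consumption) will be used to determine the" "effect of lacosamide on verbal fluency and working memory". The method is a mixed "model repeated measures approach will be used to test for differences" "in COWAT and digit span scores between the lacosamide trial and the" "placebo trial. Day and Treatment will be treated as within-subject" factors. The entry ends there. No margin, interval criterion or smallest important deficit is given in that entry or elsewhere in the document.

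Section 4.2.2 makes cognition a secondary outcome and is also neutral: the "Spatial and Digit Span tests will be used to assess the effects of lacosamide administration on cognitive function". Section 12.2 powers alcohol consumption only.

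**The concern.** A hypothesis that predicts non-significance is the null hypothesis of the test used to examine it. Hypotheses 1, 2 and 4 each predict a reduction, so imprecision works against them. Hypothesis 3 is the reverse: if a real deficit exists, fewer completers, more missing data or noisier scores all make the predicted result more likely. A non-significant p-value would be counted as support even where the confidence interval still includes a deficit that matters.

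The question is not idle in this trial. Section 3.2 gives lacosamide's cognitive profile relative to other anticonvulsants as one reason to develop it. Section 3.1 reports mixed prior evidence in patients with partial seizures: no significant COWAT change, but a significant though modest fall in Digit Span. That does not establish a deficit after eight days of dosing in heavy drinkers. It does make one possible on a test for which Hypothesis 3 predicts no significant difference.

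**Working it through.** **The logic.** Set side by side, the hypothesis cell states its prediction in terms of significance, and the analysis cell supplies only a test for a difference. No other criterion is given. Judged as written, p < 0.05 refutes Hypothesis 3 and p > 0.05 supports it. This needs no arithmetic. The figures below only show how large the effect could be.

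**Inputs.**
- n = 28, from Section 12.2, or n = 112, from the Protocol Summary. The document does not reconcile them. The summary gives 112 as the number involved, so treating all 112 as completers is a best case.
- Correlation between a subject's two trials: r = 0.6 in Section 12.2, but for total drinks. None is given for COWAT or Digit Span, so r is varied over 0.4, 0.6 and 0.8.
- Alpha 0.05, from Section 12.2. Sidedness is not stated; two-sided is assumed.
- True deficits d of 0.2, 0.3 and 0.4 between-subject SD are assumptions.

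**The plan's own figure first.** For f = 0.25, two time points and r = 0.6, the noncentrality is 0.25² × 28 × 2 / (1 − 0.6) = 8.75 on 1 and 27 df, giving power 0.814. At n = 27 power is 0.798. The plan's 28 reproduces. It equals a paired t test with standardised difference 0.5/√(2 × 0.4) = 0.559.

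**Chance of p > 0.05 when a deficit exists.** In SD units the within-subject difference has SD √(2(1 − r)). The paired t test has n − 1 df and noncentrality d√n / √(2(1 − r)). For d = 0.3, n = 28, r = 0.6 this is 0.3 × 5.292 / 0.894 = 1.775, giving power 0.402 and a 59.8% chance of non-significance. Per test:

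| n | r | d = 0.2 | d = 0.3 | d = 0.4 |
|---|---|---|---|---|
| 28 | 0.4 | 85% | 71% | 54% |
| 28 | 0.6 | 79% | 60% | 37% |
| 28 | 0.8 | 64% | 32% | 10% |
| 112 | 0.4 | 52% | 18% | 3% |
| 112 | 0.6 | 35% | 6% | 0.3% |
| 112 | 0.8 | 9% | 0.1% | <0.1% |

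Using n − 2 df, for a sequence term, changes these by at most about 0.0013.

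**What a non-significant result would leave open.** The 95% CI half-width is t(0.975, n − 1) × √(2(1 − r)/n):

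| n | r = 0.4 | r = 0.6 | r = 0.8 |
|---|---|---|---|
| 28 | 0.425 SD | 0.347 SD | 0.245 SD |
| 112 | 0.205 SD | 0.167 SD | 0.118 SD |

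At n = 28 and r = 0.6, an observed difference of exactly zero still has an interval reaching a deficit of 0.347 SD. An observed deficit just short of significance has one reaching nearly 2 × 0.347 = 0.69 SD.

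**The case against.** The strongest reply is that the faulty rule is inferred. Nowhere does the document say that p > 0.05 confirms Hypothesis 3. The analysis cell and Section 4.2.2 speak only of determining or assessing the effect. A difference test is also the analysis that would expose an impairment, and a mixed model gives an estimate and interval whether or not the plan asks for them. Hypotheses 1, 2 and 4 have no interval criterion either. No efficacy result, stopping rule or sample size depends on cognition, so this could be called a phrasing slip that careful reporting would cure.

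Much of that stands. The model is sound for estimation, the consequence is limited, and no conclusion of no impairment is prescribed. The statement about imprecision also needs its condition: with zero true difference the chance of p > 0.05 is 95% at any n, so a small or noisy trial helps the hypothesis only when a real deficit exists. And the range for a 0.3 SD deficit, 71% to 0.1%, is too wide to fix the size of the problem.

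What does not stand is the idea that neutral wording in the analysis cell repairs the hypothesis cell. The only criterion stated for Hypothesis 3 is significance. The other three hypotheses do not need an interval rule to avoid this error, because a failure to reject does not support them.

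**Conclusion.** The concern holds. As written, Hypothesis 3 treats a failure to reject as support for the absence of a difference, and the plan offers no other way to judge it. The logical fault does not depend on n or on any assumed correlation.

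Its practical size does. Under the assumed correlations, a true 0.3 SD deficit would be missed on a given test with probability 32% to 71% at n = 28, and 0.1% to 18% at 112 completers. These are illustrations, since the plan gives no variance, correlation or important difference for the cognitive tests.

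The point should be fixed, but it is confined to a secondary outcome; the primary analyses and Hypothesis 4 are untouched.

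**What to change.** Reword Hypothesis 3 as estimation of the lacosamide-minus-placebo difference. Report that difference with its 95% CI from the crossover model for each cognitive test, and state that a non-significant difference will not be taken as evidence of no impairment.

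Include Spatial Span. This is a separate inconsistency, but it is settled by the same edit: Section 4.2.2 lists the test, and Section 9 and Appendix A schedule it, yet the Hypothesis 3 analysis omits it. The CRF list in Section 11.3 names only COWAT and Digit Span, so confirm that a form exists.

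Only if a claim of no meaningful impairment is wanted, fix a positive margin m for each test before unblinding. Justify it on cognitive grounds, not from the f = 0.25 used for drinks. With higher scores meaning better performance, make the claim only if the lower 95% limit lies above −m; otherwise call the result inconclusive.

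The cost is wording and reporting; no new visits, subjects or data are needed. The downside is that the claim becomes harder to make. The chance of clearing the margin on one test, from the noncentral t with noncentrality (m − true deficit)√n / √(2(1 − r)), with illustrative margins, is:

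| n | m | True deficit | r = 0.4 | r = 0.6 | r = 0.8 |
|---|---|---|---|---|---|
| 28 | 0.3 SD | 0 | 0.29 | 0.40 | 0.68 |
| 28 | 0.5 SD | 0 | 0.64 | 0.81 | 0.98 |
| 112 | 0.3 SD | 0 | 0.82 | 0.94 | 0.999 |

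With a true 0.1 SD deficit, n = 28 and r = 0.6, it is 0.21 for m = 0.3 SD and 0.63 for m = 0.5 SD. At the smaller sample size the estimation wording alone is therefore the realistic choice unless a wide margin can be justified or the correlation is high.
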